10.9 Ophthalmologic assessments

The ophthalmologic assessments at baseline and any clinically indicated exams will be listed.

10.10 Prior and Concomitant Medications and Procedures

Prior medications and procedures taken or performed within 30 days prior to screening and prior to the first dose will be documented.

All concomitant medications and procedures (those taken or performed on or after the day of the first dose to 30 days after the last dose of study drug) will be documented.

Prior and concomitant medications will be summarized by the WHO Drug Dictionary Anatomical Therapeutic Chemical 2nd level (ATC-2) and preferred term (pharmacological subgroup ATC level 5), for the safety population. If the 2nd level term is not available, the next available level (eg, ATC-2) will be used.

The number and proportion of the patients who took each medication will be tabulated by the ATC-2 level and preferred name for concomitant medications. A patient will only be counted once within each ATC-2 code and within each preferred name.

All prior and concomitant medication data will be listed by patient.

11 STATISTICAL ANALYSIS DURING THE OPEN-LABEL ANALYSIS PERIOD

In general, the analysis methods and conventions specified in [Section 3.2](#) to [10.10](#) will be applied to the open-label analysis period, with exceptions described as below.

11.1 Analysis Sub-periods

The open-label analysis period will be further split into 2 sub-periods:

- Prior to intra-patient dose escalation
- Post intra-patient dose escalation

Days on DCC-2618 treatment within the open-label analysis period for patients that crossed over to DCC-2618 will be defined from the first dose date after crossover.

11.2 Baseline

During the open-label analysis period, Study Day will be calculated using the same reference start date as defined in [Section 3.3](#).

For the “Prior to intra-patient dose escalation” sub-period, baseline will be defined as the last non-missing value prior to the first administration of DCC-2618 150mg QD.

For the “Post intra-patient dose escalation” sub-period, baseline will be defined as the last non-missing value prior to the first administration of DCC-2618 150mg BID.

11.3 Analysis Populations

For the “Prior to intra-patient dose escalation” sub-period, the analysis population will be the safety population, including patients who have been treated with DCC-2618 but not yet at 150mg BID in the open-label period.

For the “Post intra-patient dose escalation” sub-period, the analysis population will be the safety population, consisting of patients who have been treated with DCC-2618 at 150mg BID in the open-label period.

For each sub-period, the PK population will include patients who received at least 1 dose of DCC-2618 at 150mg QD or 150mg BID and had at least 1 non-missing PK concentration in plasma reported for DCC-2618.

ITT and PP populations are not applicable to the open-label analysis period.

11.4 Efficacy Analysis

Efficacy analysis during the open-label analysis period will be explored by analysis sub-periods.

For patients who initially received placebo and subsequently crossed over to DCC-2618 treatment, PFS in the “Prior to intra-patient dose escalation” sub-period will be defined as the time interval from the date of the first dose of DCC-2618 to the earliest documented evidence of disease progression. PFS will be re-defined or censored as needed, and analyzed in a similar fashion to the primary efficacy endpoint.

For patients in the “Intra-patient dose escalation” sub-period, efficacy assessment data will be presented in listings only.

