2.3. Exploratory Objectives

- To assess the efficacy of DCC-2618 in patients after dose escalation to DCC-2618 150 mg BID
- To characterize KIT and PDGFRA gene resistance mutations (and potentially other gene mutations) and their DCC-2618-driven longitudinal mutation allele frequency changes in plasma cfDNA
- To retrospectively correlate KIT and PDGFRA mutation/s and/or their frequency (as well as of potentially other gene mutations) in baseline cfDNA with clinical benefit
- To understand potential TKI-resistance mechanisms of GIST at time of progression
- To determine concordance between KIT, PDGFRA, and other mutations in tumor and cfDNA at baseline
- To assess healthcare utilization in patients with advanced GIST who have received approved therapies

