9.2.3. Exploratory Endpoints

9.2.3.1. Efficacy

- PFS by Investigator assessment after dose escalation to DCC-2618 150 mg BID

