9.8. Statistical Methods

9.8.1. General Methods

Data collected in this study will be documented using summary tables and patient data listings. Continuous variables will be summarized using descriptive statistics (number of patients, mean, median, standard deviation, minimum, and maximum). Categorical variables will be summarized using frequencies and proportions. Time-to-event data will be summarized via Kaplan-Meier (KM) methodology using the 25th, 50th (median), and 75th percentiles with associated 2-sided 95% confidence intervals.

Unless specified otherwise, baseline measurements must be the most recent value prior to receiving the first dose of study medication. If an assessment is not available, then the last assessment prior to that visit would be used.

Medical history, adverse events, and concurrent procedures will be coded using Medical Dictionary for Regulatory Activities (MedDRA). Prior and concomitant medications will be coded using the World Health Organization Drug Dictionary.

This study will be broken into 2 periods: the randomized blinded period and the open-label portion which occurs after the study treatment unblinding at the time of disease progression based on the independent radiologic review.

The data cut-off for the primary analysis will occur when 90 PFS events have occurred. It is expected that the final analysis will occur within 6 months after the last patient is enrolled into the trial.

Unless specified, the ITT population is used for efficacy analysis and the Safety population is used for the safety analysis.

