9.8.5.4. Exploratory endpoint

9.8.5.4.1. Progression-free Survival by Investigator Assessment after Dose Escalation to DCC-2618 150 mg BID

Progression-free survival (reported in weeks) after dose escalation to 150 mg BID is defined as the interval between the date of first dose of DCC-2618 150 mg BID and the earliest documented evidence of disease progression after dose escalation to 150 mg BID, or death due to any cause. Patients who undergo surgical resection of target or non-target lesions, who have received other anticancer treatments, or patients who do not have a documented date of progression or death due to any cause will be censored at the date of the last assessment post the first dose of DCC-2618 150 mg BID or if there are no assessments post the first dose, the first dose will be used as the censor date.

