2.1.4 Exploratory Objectives

- To assess the efficacy of DCC-2618 in patients after dose escalation to DCC-2618 150 mg twice daily (BID)
- To characterize KIT and PDGFRA gene resistance mutations (and potentially other gene mutations) and their DCC-2618-driven longitudinal mutation allele frequency changes in plasma cell-free DNA (cfDNA)
- To retrospectively correlate KIT and PDGFRA mutation/s and/or their frequency (as well as of potentially other gene mutations) in baseline cfDNA with clinical benefit
- To understand potential tyrosine kinase inhibitor- (TKI) resistance mechanisms of GIST at time of progression

- To determine concordance between KIT, PDGFRA, and other genetic mutations in tumor and cfDNA at baseline
- To assess healthcare utilization in patients with advanced GIST who have received approved therapies

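### SAP 11.4 plans only listings for efficacy after escalation to 150 mg BID, so the protocol's exploratory PFS endpoint has no planned estimate and the departure is not declared

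*SAP*

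**What the plan says.** **Protocol.** The first exploratory objective in Section 2.3 is "To assess the efficacy of DCC-2618 in patients after dose escalation to DCC-2618 150 mg BID". Section 9.2.3.1 lists one exploratory efficacy endpoint, "PFS by Investigator assessment after dose escalation to DCC-2618 150 mg BID". Section 9.8.5.4.1 defines it as the "interval between the date of first dose of DCC-2618 150 mg BID and the earliest documented evidence of disease progression" after escalation, or death from any cause. It adds censoring rules, including one for patients with no assessment after the first BID dose. That section names no estimator, but Section 9.8.1 covers all such endpoints: "Time-to-event data will be summarized via Kaplan-Meier (KM) methodology", with quartiles and 95% confidence intervals.

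**SAP.** Section 2.1.4 repeats the objective, again in first place, and Section 3.6 repeats the Kaplan-Meier convention. Section 11 says that the earlier methods "will be applied to the open-label analysis period, with exceptions described as below". Section 11.4 then states such an exception: for the escalation sub-period, "efficacy assessment data will be presented in listings only". The only open-label PFS that Section 11.4 analyses is for placebo patients who cross over, before any escalation. Section 1 says that the SAP sets out its differences from the protocol's methods; none is recorded for this endpoint.

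**The concern.** A defined endpoint and a retained objective lead to no planned number. The general Kaplan-Meier convention does not fill the gap, because Section 11 gives way to its own stated exceptions.

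Two features make this look unintended. First, Section 11.5 summarises exposure, adverse events and other safety data for each sub-period, so the safety experience after escalation is tabulated while efficacy is only listed. Second, protocol 1.4.2.2 expects escalation at progression to inform an integrated safety and efficacy analysis, and a listing cannot supply the efficacy part. At stake is whether the report will contain a median, an interval and an event count for the first exploratory objective. Nothing confirmatory depends on it.

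**Working it through.** **Text comparison**

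| Item | Protocol | SAP |
|---|---|---|
| Objective: efficacy after escalation | 2.3, listed first | 2.1.4, listed first |
| Endpoint: Investigator PFS after escalation | 9.2.3.1 | none |
| Start, event and censoring rules | 9.8.5.4.1 | none |
| Kaplan-Meier summary of time-to-event data | 9.8.1 | 3.6, overridden by 11.4 |
| Planned output | follows from the rows above | listings only, 11.4 |

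Section 8 of the SAP has no post-escalation endpoint. Section 11.4 calls the sub-period by a slightly different name from Section 11.1 (without the word Post), but no other sub-period fits. The comparison decides the point; the figures below only show whether an estimate would be worth producing.

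**Reproducing the planned event count.** Inputs from protocol 9.1: medians of 4.5 and 1 month, 9 months of uniform recruitment, 6 further months of follow-up, 70 and 35 patients. I assume exponential PFS. With λ = ln 2 / median, the probability of an event by month t (t ≥ 9) is

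p(t) = 1 − [exp(−λ(t − 9)) − exp(−λt)] / (9λ)

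- DCC-2618, t = 15: p = 0.7853; 70 × 0.7853 = 55.0
- Placebo, t = 15: p = 0.9975; 35 × 0.9975 = 34.9
- Total 89.9, which agrees with the stated 90 (55 + 35).

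**The same count with 80 and 40 patients and no dropout.** At month 15 this gives 62.8 + 39.9 = 102.7 events. The data cut comes at 90 events (protocol 9.8.1, SAP 3.1), so month 15 is past it. Solving 80·p₁(t) + 40·p₂(t) = 90 gives t ≈ 11.6 months:

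- DCC-2618: 80 × 0.638 = 51.0
- Placebo: 40 × 0.974 = 39.0

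So about 51 to 55 DCC-2618 PFS events are expected at the cut.

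**From events to escalators.** This range is an upper bound on escalators from the DCC-2618 arm by the cut. It includes deaths, escalation is optional (protocol 3.1), and protocol 5.3.2 has dose-reduced patients stop study drug once progression is confirmed. Placebo patients who cross over and later escalate would add to it. The documents give no escalation rate.

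**Precision, under assumed numbers of escalators**

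- 30 escalators, Kaplan-Meier estimate of 50%, no censoring: 1.96 × √(0.25/30) = 0.179, or about ±18 points. Censoring widens this.
- 20% to 80% of 55 escalate (11 to 44 patients) and 50% to 100% of them have an event: d = 5.5 to 44 events. The approximate 95% limits for an exponential median are the median divided and multiplied by exp(1.96/√d), a factor of about 2.3 (fewest events) to 1.3 (most).

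A descriptive estimate is feasible over most of this range and imprecise at the low end.

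**The case against.** The best defence is that little turns on this. The endpoint is exploratory, open-label and uncontrolled, and it sits outside the sequence in protocol 9.6 and SAP 8.5. A median in self-selected escalators would support no efficacy claim, and the SAP states the listings choice openly. All of this stands and limits the weight of the point. It does not explain why the objective is kept while its endpoint is dropped, or why the difference is not declared.

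A reader might infer that any later summary would be devised after the data are seen. The documents do not support that. Protocol 9.8.5.4.1 already fixes the start, events and censoring, and 9.8.1 fixes the estimator. A summary that followed them would be pre-specified. What is missing is the SAP's commitment to produce it.

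A reader might also infer that SAP version 2 removed the analysis. The summary of changes shows otherwise: version 1 placed all open-label efficacy in listings, and version 2 added crossover PFS while keeping listings for escalation. The reduction is relative to the protocol only.

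Finally, the SAP is based on protocol Amendment 5, and the amendment number of the protocol reviewed cannot be confirmed with its title pages removed. The mismatch between SAP 2.1.4 and 11.4 stands regardless.

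**Conclusion.** The point holds as a minor inconsistency. The SAP keeps the objective of assessing efficacy after escalation but commits to no estimate for it, against the protocol's endpoint, definition and general method, and without declaring the change. The primary result, the key secondary result and type I error are unaffected.

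The size is uncertain. The bound of about 51 to 55 DCC-2618 PFS events rests on exponential PFS, the protocol's medians and recruitment, and a cut at 90 events. It would be wrong to count these as progressions, since deaths are included, or to take the 62.8 events at month 15 for 80 patients, since the cut would already have occurred. The ±18 points rests on an assumed 30 escalators and is a best case.

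**What to change.** Replace the listings-only sentence in SAP 11.4 with a descriptive Kaplan-Meier summary of Investigator-assessed PFS from the first 150 mg BID dose:

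- use the event and censoring rules of protocol 9.8.5.4.1;
- report number at risk, events, and quartiles with 95% confidence intervals;
- show it separately by initial randomised arm, because protocol 5.2.1 bases the progression that precedes escalation on independent review in patients randomised to DCC-2618 and on Investigator assessment in crossover patients;
- label it exploratory and uncontrolled.

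The listings can stay alongside. If the sponsor prefers listings alone, the SAP should at least declare and justify the departure as its Section 1 promises; that would settle the inconsistency but leave the objective without an estimate.

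The cost is a wording change and one extra table. Investigator response is already recorded in the eCRF (protocol 6.10.1), and SAP 11.2 and 11.3 already define the baseline and population for this sub-period. The downside is an imprecise estimate if few patients escalate.

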11.5 Safety Analysis

Exposure to DCC-2618 will be summarized by analysis sub-periods. The duration of DCC-2618 in weeks, total dose, average daily dose, and relative dose intensity will be displayed using continuous descriptive statistics. In addition, the number and percent of patients in categories by treatment duration and patients with a dose increase, reduction, and interruption will be summarized.

All the AEs and the other safety data collected during the open-label analysis period will be analyzed. All the AEs in the open-label analysis period will be analyzed as TEAEs.

TEAEs and the other safety endpoints will be analyzed by treatment groups as defined by patients' initial treatment in the double-blind treatment period, for all patients who entered in the open-label analysis period overall and separately for each sub-period.

12 QUALITY CONTROL

All data displays and analyses will adhere to the International Conference on Harmonisation (ICH) Harmonized Tripartite Guideline: Structure and Content of Clinical Study Reports (ICH Topic E3).

The sponsor will review all tables, listings, and figures prior to final database lock. Final SAS datasets, programs and outputs will be transferred to the sponsor at project completion.

